7.3.1 Main analyses

A) Patient characteristics influencing choice of antithrombotic treatment for stroke prevention at baseline

Demographics and baseline characteristics (including specifically stroke/bleeding risk scores (CHADS₂, CHA₂DS₂-VASc and HAS-BLED, see [Appendix 10.1](#))) will be summarized descriptively for all eligible patients by antithrombotic treatment choice for stroke prevention at the baseline visit.

The antithrombotic treatment choice for stroke prevention at the baseline visit (e.g. none, VKAs, ASA, clopidogrel, dabigatran, etc.) will be described.

Potential channeling bias between patients initiating dabigatran and VKA at the patient's baseline visit will be explored using comparisons of important baseline characteristics (known risk factors for stroke and bleeding, e.g. age, gender, hypertension, diabetes mellitus, prior stroke, prior transient ischemic attack, prior bleeding and concomitant medication use) between the two groups at regular intervals during Phase II and Phase III. This includes the generation of two-way comparisons for each of the baseline characteristics (dabigatran versus VKA) and calculation of a propensity score using multiple regression models to predict the probability of treatment choices (see also interim analyses [7.3.4](#)).

B) Important outcome events (Phase II only)

Incidence rates and cumulative risks over time since initiation with 95%-confidence intervals for important outcome events (see [Section 5.1](#).) will be calculated within the dabigatran cohort. In addition these analyses will be done stratified by chronic antiplatelet treatment at baseline. The analysis will be based on all eligible patients initiating dabigatran for stroke

Proprietary confidential information.

© 2014 Boehringer Ingelheim International GmbH or one or more of its affiliated companies. All rights reserved.

This document may not - in full or in part - be passed on, reproduced, published or otherwise used without prior written permission.

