$$[\lambda_{\text{lower}}, \lambda_{\text{upper}}] = [\{0.5 \chi^2(\alpha/2; 2x)\}/n, \{0.5 \chi^2(1-\alpha/2; 2x+2)\}/n],$$

where $\chi^2(\gamma, r)$ is the 100 γ th percentile of a chi-square distribution with r degrees of freedom, n is the patient years under risk for the event, x is the number of patients with event, and α for (1- α) % 2-sided CIs.

Cumulative risk is defined as cumulative proportion of patients with event and will be calculated as the Kaplan-Meier estimate for failure. The Kaplan-Meier curve will be plotted. The proportion of patients with event, as well as the proportion of censored patients falling into specified intervals and the Kaplan-Meier estimate for failure will be computed for the following categories:

- ≤ 3 months
- $3 < \text{and } \leq 6$ months
- $6 < \text{and } \leq 12$ months
- $12 < \text{and } \leq 18$ months
- $18 < \text{and } \leq 24$ months
- $24 < \text{and } \leq 30$ months
- > 30 months

In the following if not stated otherwise for all analyses only patients from the restricted patient set are considered. Furthermore only the first treatment period is included (i.e. as-treated analysis) if not mentioned otherwise (like e.g. for ITT analyses).

- 1) Main analysis of composite outcome (Stroke, systemic embolism, myocardial infarction, life-threatening bleeding events and vascular death)

Acknowledging the limited precision given the sample size and the potential limitations, for the main comparison of the two treatment groups, Dabigatran and VKA, with regards to the composite outcome a multivariable Cox regression model (according to the 1160.129 and 1160.136 protocols) will be performed if those patient groups are determined to be comparable in terms of the PS analysis. The multivariable Cox regression model will include the following variables as core variables: treatment, age (<65 , $65-75$, >75), gender and the following main stroke and bleeding risk factors: prior bleed, previous stroke/TIA, previous myocardial infarction, abnormal kidney function and concomitant antiplatelets use. The following further covariates will be investigated within a model selection procedure: (sub)region, congestive heart failure, left ventricular

hypertrophy, systemic embolism, complex aortic plaque, hypertension, diabetes mellitus, PAD, CrCl, NSAID use type of AF, hepatic disease, alcohol abuse, any drug (HAS-BLED), previous OAC use (within 3 months), smoking status, and concomitant medication like antipsychotics.

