- j. The main analysis might be repeated using a different composite outcome definition: replacing vascular death with all cause death in the composite outcome
- k. One more sensitivity analysis might be performed by repeating the main analysis using different definitions of washout and gap for treatment discontinuation

3) Analyses of other outcome events

The following Cox models will only be performed if enough events are reported such that the number of events is roughly proportional to the number of degrees of freedom for all the covariates included in the Cox model. If for other kind of outcome events not listed below

enough events are reported a similar kind of analysis might be performed. The same model selection procedure approach as used for the composite outcome will be used. For all models below the following rule of thumb applies as in the main model used for the composite outcome. The number of degrees of freedom for all covariates in the model * 10 roughly shall not exceed the number of events reported for the composite outcome. The PS matched pair analysis on the specific outcome event might be performed for all outcomes. Additional sensitivity analyses for the single outcome events similar to the ones described for the composite outcome under 2) a),c),f) will be performed if the number of events reported is large enough and additional above mentioned sensitivity analysis will be considered.

- *Composite vascular outcome*

Using the same methods as described above for the composite outcome under 1), VKA and Dabigatran treated patients will be compared in terms of the vascular composite outcome using the same approach for the main analysis and the same sensitivity analyses a), c), f), and i) as outlined for the composite outcome above. Additional above mentioned sensitivity analysis might be considered.

- *Stroke/SEE (optional)*

For stroke/SEE events the multivariable Cox model will include the following variables as core variables as used for the composite outcome: treatment, age (<65, 65-<75, >=75), gender and stroke and bleeding risk factors: prior bleed, previous stroke/TIA, previous myocardial infarction, abnormal kidney function, and concomitant antiplatelet use.

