Further covariates will be selected within the model selection procedure: (sub)region, congestive heart failure, left ventricular hypertrophy, systemic embolism, complex aortic plaque, hypertension, diabetes mellitus, PAD, CrCl, NSAID use (including missing/unknown as a separate category), type of AF, complex aortic plaque, hepatic disease, alcohol abuse, any drug (HAS-BLED), smoking status, concomitant medication like antipsychotics, previous OAC use (within 3 months).

A similar model might be run on stroke events alone if the number of events reported is large enough.

- *Major Bleeding*

For the major bleeding outcome event the multivariable Cox model will include the following variables as core variables: treatment, age (<65, 65-<75, >=75), gender and the following bleeding risk factors: prior bleed, abnormal kidney function, any drug-HAS-BLED, and concomitant antiplatelet use. Further covariates will be selected within a model selection procedure: (sub)region, congestive heart failure, previous stroke/TIA, previous myocardial infarction, left ventricular hypertrophy, systemic embolism, complex aortic plaque, hypertension, diabetes mellitus, PAD, CrCl, NSAID use (including missing/unknown as a separate category), type of AF, complex aortic plaque, hepatic disease, alcohol

abuse, smoking status, concomitant medication like antipsychotics, previous OAC use (within 3 months).

- *All Cause Death (optional)*

For death events the multivariable Cox model will include the following variables as core variables like used for the composite outcome: treatment, age (<65, 65-<75, >=75), gender and the following main stroke and bleeding risk factors: prior bleed, previous stroke/TIA, previous myocardial infarction, abnormal kidney function and concomitant antiplatelets use. Further covariates will be selected within a model selection procedure: (sub)region, congestive heart failure, left ventricular hypertrophy, systemic embolism, complex aortic plaque, hypertension, diabetes mellitus, PAD, CrCl, NSAID use (including missing/unknown as a separate category), type of AF, complex aortic plaque, hepatic disease, alcohol abuse, any drug (HAS-BLED), smoking status, concomitant medication like antipsychotics, previous OAC use (within 3 months).

- *Myocardial Infarction (optional)*

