For MI events the multivariable Cox model will include the following variables as core variables: treatment, age (<65, 65-<75, >=75), gender and the following MI risk factors (hypertension, diabetes mellitus, previous myocardial infarction) and concomitant antiplatelet use. Further covariates will be selected within a model selection procedure: (sub)region, left ventricular hypertrophy, systemic embolism, complex aortic plaque, congestive heart failure, PAD, CrCl, NSAID use (including missing/unknown as a separate category), type of AF, complex aortic plaque, hepatic disease, alcohol abuse, any drug (HAS-BLED), smoking status, concomitant medication like antipsychotics, previous OAC use (within 3 months).

If sample size allows, comparisons of other outcomes may be considered for either 1160.129 or 1160.136, if needed.

Dependent on the number of patients receiving different antithrombotic treatment for stroke prevention and dependent on comparability of important baseline characteristics, other pairwise comparisons of the treatment regimes regarding outcome events might be performed similar to the analysis as outlined for Dabigatran and VKA if the total number of events does allow for a meaningful comparison.

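### The optional MI Cox model lists previous stroke/TIA and prior bleed neither as core nor as candidate covariates, unlike every other listed outcome model

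*SAP*

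**What the plan says.** SAP 7.6, item 3, defines a separate Cox model for each further outcome. Each has a forced core and a list of further covariates for selection.

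For myocardial infarction, marked optional, the core is treatment, age in three bands, gender and "the following MI risk factors (hypertension, diabetes mellitus, previous myocardial infarction) and concomitant antiplatelet use". The candidates begin "sub)region, left ventricular hypertrophy, systemic embolism, complex aortic plaque, congestive heart failure, PAD, CrCl, NSAID use", continue with type of AF, and end with "hepatic disease, alcohol abuse, any drug (HAS-BLED), smoking status, concomitant medication like antipsychotics, previous OAC use (within 3 months".

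The composite model (item 1) forces in "prior bleed, previous stroke/TIA, previous myocardial infarction, abnormal kidney function and concomitant antiplatelets use". The stroke/SEE model forces in "prior bleed, previous stroke/TIA, previous myocardial infarction, abnormal kidney function, and concomitant antiplatelet use", and the all-cause-death model uses the same set. The major-bleeding core is different, "prior bleed, abnormal kidney function, any drug-HAS-BLED, and concomitant antiplatelet use", but its candidate list takes up what was displaced: "Further covariates will be selected within a model selection procedure: (sub)region, congestive heart failure, previous stroke/TIA, previous myocardial infarction".

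Under item 1, a candidate enters only if it changes the treatment hazard ratio by more than 10%, subject to ten events per degree of freedom. Item 3 applies the same selection procedure to the other outcomes.

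Protocol 7.3.1 A) includes "prior stroke, prior transient ischemic attack, prior bleeding and concomitant medication use" among the baseline characteristics to be compared between dabigatran and VKA initiators when channeling bias is explored. Protocol 3.1 and 3.2.1 repeat the list.

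**The concern.** When the major-bleeding paragraph changes its core, it moves the displaced risk factors into the candidate list, so nothing is lost. The MI paragraph replaces prior bleed, previous stroke/TIA and abnormal kidney function with hypertension and diabetes, and moves none of the three to the candidates. The SAP gives no reason, which suggests an oversight in drafting.

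The selection rule cannot repair this, because a variable outside the list is never tried. If dabigatran and VKA patients in the analysis set still differ in previous stroke/TIA, and previous stroke/TIA is associated with MI, the multivariable MI hazard ratio carries that difference however large it is. Previous stroke/TIA is the main concern. The documents give no MI-specific argument for prior bleed, whose case rests on the protocol's channeling list and on consistency with the other models.

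**Working it through.** **Step 1: compare the lists.** The plan states no figure for the MI model, so there is none to reproduce. Status of each variable in SAP 7.6:

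| Model | Previous stroke/TIA | Prior bleed | Previous MI | Abnormal kidney function |
|---|---|---|---|---|
| Composite | core | core | core | core |
| Stroke/SEE | core | core | core | core |
| All-cause death | core | core | core | core |
| Major bleeding | candidate | core | candidate | core |
| MI | absent | absent | core | absent (CrCl is a candidate) |

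The vascular composite follows the composite's method. Taking core and candidates together, the composite list minus the major-bleeding list is empty. The composite list minus the MI list is previous stroke/TIA, prior bleed and abnormal kidney function. CrCl covers the last of these. Nothing in the MI list replaces the other two: systemic embolism is a separate item, and the HAS-BLED drug item is not bleeding history.

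**Step 2: what else could adjust for them.**

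- SAP 7 trims the analysis set on the propensity score and keeps the region of overlap. This restricts the sample but does not adjust within it.
- SAP 7.6 item 3 extends 2a) (propensity-score stratification) and 2c) (matching) to single outcomes if events are numerous enough. Item 2c) adds an optional Cox model with covariates that remain imbalanced after matching.
- These routes work by design only if the two variables are in the propensity-score model. That model is specified in a separate plan not supplied here.
- Item 2f) might bring in a stroke risk factor through an interaction term. It is optional and explores effect modification; it does not change the main MI model.
- For 1160.136, item 2 limits the composite's sensitivity analyses to d) and f), and the opening of 7.6 repeats for the EU study only analyses on the restricted and eligible sets. Whether 2a) would be run for MI there is not stated.

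**Step 3: possible size.** The documents give neither prevalence by treatment group nor an association with MI, so all inputs here are assumed. Let p0 and p1 be the prevalence of previous stroke/TIA in the two groups and h its hazard ratio for MI. The crude distortion factor is

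(1 + p1(h − 1)) / (1 + p0(h − 1)).

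With p0 = 10%:

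| p1 | h = 1.5 | h = 2.0 | h = 2.5 |
|---|---|---|---|
| 15% | 1.075/1.05 = 1.024 | 1.15/1.10 = 1.045 | 1.225/1.15 = 1.065 |
| 20% | 1.10/1.05 = 1.048 | 1.20/1.10 = 1.091 | 1.30/1.15 = 1.130 |
| 25% | 1.125/1.05 = 1.071 | 1.25/1.10 = 1.136 | 1.375/1.15 = 1.196 |

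Three of the nine combinations exceed 10%. The central one, 1.09, does not.

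**Step 4: cost in degrees of freedom.** The MI core has treatment 1 + age 2 + gender 1 + hypertension 1 + diabetes 1 + previous MI 1 + antiplatelet use 1 = 8 df, or 80 events at ten per df. If both added candidates were selected, this becomes 10 df and 100 events. If neither is selected, nothing changes.

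**The case against.** The strongest reply is that outcome-specific covariates may be intended. The paragraph calls its core MI risk factors, and the major-bleeding core also differs from the composite's. The protocol presents prior stroke, TIA and bleeding as risk factors for stroke and bleeding, not for MI, and does not require them in every outcome model. This stands as a possible reason, but the SAP does not state it. It also explains a different core better than it explains leaving the variables out of the candidate list.

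The size may also be small. The comparison is run only if the groups are judged comparable on the propensity score. The assumed prevalences correspond to standardized differences of about 0.15, 0.28 and 0.40, against the 0.10 that SAP 7.6 item 2c) uses to flag imbalance after matching, so the upper rows are pessimistic. The formula also ignores adjustment for age, hypertension, diabetes, previous MI and antiplatelet use. All of this stands. In the central case a candidate would not meet the 10% rule and the reported hazard ratio would not change.

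Three stronger readings are tempting, and the documents support none of them:

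- A reader might infer that the two variables can never be adjusted for in the MI comparison. That is true only of the multivariable Cox model; the propensity-score analyses in step 2 may reach them.
- A reader might infer a bias well beyond the 10% rule. The inputs are assumed, and most combinations fall below it.
- A reader might infer that the MI hazard ratio cannot be set beside the others. Selection is run separately for each outcome, so the final models may differ anyway, and both composites that contain MI force these variables in.

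**Conclusion.** The omission is real and can be confirmed by reading: of the outcome models listed in SAP 7.6, only the MI model cannot take in previous stroke/TIA or prior bleed. The multivariable MI hazard ratio therefore cannot adjust for two characteristics that the protocol names for channeling, whatever their effect on the estimate. Support from propensity-score analyses is conditional in the global study and doubtful in 1160.136, and it assumes that both variables are in a propensity-score model that could not be seen.

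The size of any bias is unknown; 1.02 to 1.20 only illustrates it under the assumptions in step 3. The importance is minor: the model is optional, depends on event numbers, and belongs to a study for which Protocol 7.2 foresees no confirmatory testing.

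**What to change.** In the myocardial infarction paragraph of SAP 7.6 item 3, add previous stroke/TIA and prior bleed to the further covariates, as the major-bleeding paragraph does for previous stroke/TIA and previous MI. If the omission is deliberate, state the reason there instead. Abnormal kidney function need not be added, since CrCl is already a candidate and SAP 7.6 itself cautions against highly correlated covariates.

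The cost is one line of text. Both variables are already needed for the other models, and as candidates they use no degrees of freedom unless selected; each one selected then needs ten more events under the SAP's rule.

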7.8 EXPOSURE TIME

Exposure data will be summarized based on all eligible patients by antithrombotic treatments. Furthermore exposure data for all patients in the matched and restricted patient sets will be provided for Dabigatran and VKA patients. Prescribed but never taken patients will be excluded from all the analyses described in this section.

A patient might receive several mono-/combined therapies during study conduct. Total exposure time will be calculated for each treatment group X based on all treatment periods (see [Section 6.1](#) for definition of treatment groups) as:

Exposure treatment X[days] = $\sum_{\text{treatment-period with treat= x}} (\text{treatment stop date} - \text{treatments start date} + 1)$.

The calculated days are converted to months (12*days/365.25) for summary tables.

In addition, total subject years will be calculated and presented:

Total subject – years treatment X[years] = $\sum_{\text{subjects}} \text{Exposure treatment X [days]} / 365.25$.

Descriptive statistics of the (cumulative) treatment exposure in months and the percentage of patients falling into specified intervals will be provided. The following categories might be used

<=14 days

14 days < and <=1 month

1< and <=3 months

3< and <=6 months

6< and <=9 months

9< and <=12 months

12< and <=16 months

16< and <=20 months

20< and <=24 months

>24 months

7.9 SAFETY ANALYSIS

7.9.1 Adverse events

7.9.1.1 Death

See analysis of important outcome events and standard adverse event (AE) analyses respectively

7.9.1.2 Bleeding

See analysis of important outcome events and standard AE analyses respectively

7.9.1.3 Interventions

See additional analyses

7.9.1.4 Other standard AE analyses

Analyses for AEs will be based on all patients treated with an anticoagulant treatment at least once. The analysis of adverse events will be descriptive in nature and will be based on BI standards (see DM&SM: Handling and summarization of adverse event data for clinical trial reports and integrated summaries [\[4\]](#)). Adverse events will be coded with the most recent version of MedDRA. The summary of standard AE tables will be based on the AE/ SAE CRFs. According to the reporting procedures for this study, all SAEs and outcome events are to be documented on the SAE or OE form irrespective of causal relationship to antithrombotic treatment or any other BI drug. Non-serious AEs which are not deemed related to antithrombotic treatment or to any other BI drug should not be included in the CRF (see study protocol, Section 5.2.2.2).

For the analysis, only AEs which are considered treatment-emergent for antithrombotic treatment are included (see [Section 6.1.2](#) for definition of analysis periods for AEs). AEs which are assigned to treatment other than the ones listed in [Table 6.1:1](#) (besides the no treatment group), to post-study, or to pre-treatment will not be displayed in summary tables but will only be reported in listings (sorted by analysis period (pre-treatment, , post-study, on-treatment) and antithrombotic treatment).

For analysis of adverse drug reactions (ADRs), all AEs which are related to antithrombotic therapy according to the investigators judgment are to be included.

The following tables will be created by treatment group:

- Overall summary of ADRs and serious adverse events
- Frequency [N (%)] and incidence rate (per 100 patient years) of patients with SAEs
- Frequency [N (%)] and incidence rate (per 100 patient years) of patients with SAEs leading to death

- Frequency [N (%)] and incidence rate (per 100 patient years) of patients with ADRs (related to antithrombotic therapy)
- Frequency [N (%)] and incidence rate (per 100 patient years) of patients with ADRs (events related to antithrombotic therapy prescribed at baseline)
- Frequency [N (%)] and incidence rate (per 100 patient years) of patients with ADRs (related to antithrombotic therapy) leading to discontinuation of antithrombotic treatment
- Frequency [N (%)] and incidence rate (per 100 patient years) of patients with ADRs (related to antithrombotic therapy) leading to hospitalization.
- Frequency [N (%)] and incidence rate (per 100 patient years) of patients with ADRs (related to antithrombotic therapy) leading to death
- Frequency [N (%)] and incidence rate (per 100 patient years) of patients with Serious ADRs (related to antithrombotic therapy)

Time at risk and incidence rates will be calculated according to BI standards (see DM&SM: Handling and summarization of adverse event data for clinical trial reports and integrated summaries [\[4\]](#); especially the washout period will be included in calculation of time at risk up to the time point at which other relevant antithrombotic treatment is started).

Additionally a summary of patients with non-serious adverse events with overall occurrence above 5% will be created for the Appendix of the study report.

